8.2.4.2. Laboratory Data

For the purposes of summarization in both the tables and listings, all laboratory values will be converted to standardized units. If a lab value is reported using a non-numeric qualifier (eg, less than (<) a certain value, or greater than (>) a certain value), the given numeric value will be used in the summary statistics, ignoring the non-numeric qualifier.

Laboratory test results will be summarized according to the scheduled sample collection time point. Change from baseline will also be presented. Unscheduled laboratory test results will be listed and included in laboratory shift tables. The parameters to be analyzed are as follows:

- Hematology: hemoglobin, hematocrit, RBC, neutrophils, lymphocytes, monocytes, eosinophils, basophils, platelets, and white blood cell (WBC) count
- Serum chemistry: electrolytes (sodium, potassium, and chloride), CO₂, calcium, phosphorus, magnesium, total protein, albumin, glucose, serum creatinine, urea, AST, ALT, LDH, alkaline phosphatase, total and direct bilirubin, and uric acid.

Shift tables will be constructed for laboratory parameters to tabulate changes in NCI CTCAE for toxicity (version 4.0) from baseline to post baseline worst CTC grade. Parameters to be tabulated will include:

- Hematology: hemoglobin, platelets, WBC, ANC
- Serum chemistry: ALT, AST, alkaline phosphatase, creatinine, total bilirubin, calcium, magnesium, potassium, sodium, and phosphate.

Summary statistics will also be presented for shift from baseline urinalysis values.

- Urinalysis: protein, specific gravity, glucose, and occult blood

Listings to be presented include hematology, serum chemistry, and urinalysis. These will include the test result, units, normal range (H and L), change from baseline, and CTCAE grades if graded.

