4.5 Dose-Limiting Toxicity

A DLT is defined by the occurrence of any of the following toxicities possibly, probably or definitely related to BBI608 or BBI608 in combination with TMZ during the first 28 days of combination treatment:

- CTCAE Grade 3 thrombocytopenia with clinically significant bleeding
- CTCAE Grade 4 hematological toxicity.
- CTCAE Grade 3 non-hematological toxicity, except:
 - Grade 3 nausea, vomiting, anorexia, diarrhea or fatigue that persist < 7 days with appropriate supportive care.
- CTCAE Grade 4 non-hematological toxicity
 - Because DVT and PE are common complications among GBM patients, the first occurrence of DVT or PE will not be considered a DLT.
- Toxicities leading to delay of study treatment for ≥ 14 days
- During the post-surgical period and prior to initiation of combination therapy with BBI608 and TMZ, any grade 3 or greater hematological or non-hematological toxicity that cannot be attributed to the surgical procedure or to typical post-operative complications
- Any other toxicity that in the view of the Principal Investigator represents a clinically significant hazard to the patient

Whether a DLT has occurred will be assessed during the 28 days of the first cycle of combination treatment with TMZ and during the run in and post-operative period of Arm A. DLT will be determined from adverse events and changes from baseline in physical examination findings and in laboratory parameters.

To be considered evaluable for DLT, compliance with the assigned dose of BBI608 and TMZ must be $\geq 80\%$. Patients who do not complete 28 days of combination therapy for reasons other than DLT or patients who are not eligible for DLT assessment may be replaced. Adverse events considered related to TMZ only will not be considered DLTs for BBI608 in combination with TMZ.

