6.3 Clinical Laboratory Tests

Safety laboratory determinations will include hematology, blood chemistry, and urinalyses. All laboratory tests required during the study must be obtained at a primary laboratory designated by the Principal Investigator.

- Hematology: CBC including hemoglobin, white blood cell count with 5-part differential, platelets
- Biochemistry: electrolytes (sodium, potassium, and chloride), CO₂, calcium, phosphorus, magnesium, total protein, albumin, glucose, and serum creatinine, blood urea nitrogen (BUN), AST, ALT, lactate dehydrogenase (LDH), alkaline phosphatase, total and direct bilirubin, and uric acid
- Routine urinalysis: dipstick including protein, specific gravity, glucose and blood
- Serum pregnancy test for female patients of childbearing potential

MGMT methylation status: MGMT promoter methylation status will be assessed on archival tumor tissue submitted at enrollment, as well as tumor tissue obtained during the course of the study (i.e. specimen from surgical resection)

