7.2.2 Temozolomide

Serious toxicities attributable to TMZ include neutropenia, thrombocytopenia, lymphopenia, *pneumocystis* pneumonia, and hepatotoxicity. Common adverse side-effects of TMZ include nausea and vomiting. Please see the Package Insert for full prescribing and toxicity information.

Cycle 1: Dosage in Cycle 1 (maintenance) is 150 mg/m² once daily for 5 days followed by 23 days without treatment. Cycles 2-6:

At the start of Cycle 2, the dose can be escalated to 200 mg/m², if the CTC non-hematologic toxicity for Cycle 1 is Grade less than or equal to 2 (except for alopecia, nausea, and vomiting), absolute neutrophil count (ANC) is greater than or equal to 1.5 x 10⁹ /L, and the platelet count is greater than or equal to 100 x 10⁹ /L.

The dose remains at 200 mg/m² per day for the first 5 days of each subsequent cycle except if toxicity occurs. If the dose was not escalated at Cycle 2, escalation should not be done in subsequent cycles.

Dose Reduction or Discontinuation:

Dose reductions should be applied according to Tables 2 and 3.

During treatment, a complete blood count should be obtained on Day 22 (21 days after the first dose of TEMODAR) or within 48 hours of that day, and weekly until the ANC is above 1.5 x 10⁹ /L (1500/μL) and the platelet count exceeds 100 x 10⁹ /L (100,000/μL).

The next cycle of TEMODAR should not be started until the ANC and platelet count exceed these levels. Dose reductions during the next cycle should be based on the lowest blood counts and worst non-hematologic toxicity during the previous cycle.

Dose discontinuations should be applied according to Tables 2 and 3.

Table 2: Temozolomide Dose Levels for Maintenance Treatment

Dose Level	Dose (mg/m ² /day)	Remarks
-1	100	Reduction to prior toxicity
0	150	Dose during Cycle 1
1	200	Dose during Cycles 2-6 in absence of toxicity

Table 3: Temozolomide Dose Reduction or Discontinuation During Maintenance Treatment

[figure not shown]
Toxicity	Reduce TMZ by 1 Dose Level*	Discontinue TMZ
Absolute Neutrophil Count	Less than 1.0 x 10	See footnote†
Platelet Count	Less than 50 x 10	See footnote†
C Nonhematological Toxicity (except for alopecia, nausea, vomiting)	CTC Grade 3	CTC Grade 4

*TMZ dose levels are listed in Table 2.

† TMZ is to be discontinued if dose reduction to less than 100 mg/m² is required or if the same Grade 3 nonhematological toxicity (except for alopecia, nausea, vomiting) recurs after dose reduction. TMZ=temozolomide; CTC=Common Toxicity Criteria.

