8.1.2 Definitions

An adverse event (AE) is defined as any untoward medical occurrence in a patient or clinical investigation subject that does not necessarily have a causal relationship with this treatment. An AE can therefore be any unfavorable and unintended sign (including an abnormal laboratory finding), symptom, or disease temporally associated with the use of a medicinal (investigational) product, whether or not considered related to the medicinal product.

Laboratory data are to be collected as stipulated in this protocol, and toxicity trends will be analyzed utilizing objective toxicity criteria. Clinical syndromes associated with laboratory abnormalities are to be recorded as appropriate (e.g., diabetes mellitus instead of hyperglycemia).

Progression of disease is considered an efficacy outcome parameter and should not be captured as an AE. A non-serious AE is any untoward medical occurrence that does not meet any of the criteria for SAEs as defined below.

Patients should be instructed to report any AE that they experience to the Investigator. Investigators should assess the patient for AEs at each visit. AEs occurring during the clinical trial and the follow-up period should be recorded on the appropriate AE CRF. To

capture the most potentially relevant safety information during a clinical trial, it is important that investigators record accurate AE terms on CRFs.

Wherever possible, a specific disease or syndrome rather than individual associated signs and symptoms should be identified by the investigator and recorded on the CRF. However, if an observed or reported sign or symptom is not considered a component of a specific disease or syndrome by the investigator, it should be recorded as a separate AE on the CRF.

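### The haematology CTCAE shift tables do not name lymphocytes, so no planned laboratory-based table counts patients by worst lymphopenia grade

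*SAP*

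**What the plan says.** **Shift tables.** SAP 8.2.4.2 plans tables of the change in CTCAE v4.0 grade from baseline to the worst later grade. The list opens with "Parameters to be tabulated will include", and its haematology line is "Hematology: hemoglobin, platelets, WBC, ANC".

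**Summaries by time point.** The same section has a longer list for descriptive statistics and change from baseline: "Hematology: hemoglobin, hematocrit, RBC, neutrophils, lymphocytes, monocytes, eosinophils, basophils, platelets, and white blood cell (WBC) count". Lymphocytes are in that list.

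**Listings.** The section also plans listings of haematology, chemistry and urinalysis: "These will include the test result, units, normal range (H and L), change from baseline, and CTCAE grades if graded". Unscheduled results go into the listings and the shift tables; the summaries follow scheduled time points.

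**Collection.** Protocol 6.3 specifies "CBC including hemoglobin, white blood cell count with 5-part differential, platelets", so lymphocyte counts are available.

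**Why lymphocytes matter here.** Protocol 7.2.2: "Serious toxicities attributable to TMZ include neutropenia, thrombocytopenia, lymphopenia". Protocol 4.5 includes "CTCAE Grade 4 hematological toxicity" among the dose-limiting toxicities, with no exception for lymphopenia.

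**Adverse event recording.** Protocol 8.1.2 counts an abnormal laboratory finding as a possible adverse event, and adds: "Clinical syndromes associated with laboratory abnormalities are to be recorded as appropriate". It also says that laboratory toxicity trends will be analysed with objective toxicity criteria.

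**The concern.** Protocol 7.2.2 names three blood-count toxicities of TMZ in one sentence. Two of them have a row in the shift table and the third has none. The SAP gives no reason for the difference.

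The shift table is the only planned table that counts patients by grade directly from laboratory values. It does not depend on whether an investigator reported the finding or on how it was attributed. For lymphocytes, the protocol's intention to analyse laboratory toxicity by objective criteria therefore has no table behind it.

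Safety and tolerability of the combination are the Phase Ib primary objective (protocol 2.1, SAP 2.2.1). A reader of the study report would want to know how many patients had Grade 3 or 4 lymphopenia, and would have to count them by hand from a listing.

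**Working it through.** No power, alpha or sample-size figure is involved, so the check is a comparison of texts with one small piece of arithmetic.

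**1. The two parameter lists in SAP 8.2.4.2.** The time-point summaries name 10 haematology parameters, lymphocytes among them. The shift tables name 4, lymphocytes not among them.

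**2. The TMZ toxicities in protocol 7.2.2 against the shift-table rows.**

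| Toxicity named | Shift-table row |
|---|---|
| Neutropenia | ANC |
| Thrombocytopenia | Platelets |
| Lymphopenia | None |

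**3. What each planned output shows for lymphopenia.**

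| Output | Shows a grade? | Counts patients by worst laboratory grade? |
|---|---|---|
| Time-point summaries (SAP 8.2.4.2, with statistics as in 8.1.3) | No. Mean, SD, median, minimum, maximum | No; scheduled values only |
| Haematology listing (SAP 8.2.4.2) | Yes, if the parameter is graded | No; one line per result |
| TEAE tables by preferred term and maximum grade (SAP 8.2.4.1) | Yes, if reported as an adverse event | Counts reported events, not laboratory values |
| DLT listing (SAP 8.2.2.1) | Only for events that qualify as DLTs | No |
| Shift table (SAP 8.2.4.2) | Not for lymphocytes as listed | Not for lymphocytes as listed |

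An unscheduled low lymphocyte count therefore reaches the listing but no laboratory table. For ANC or platelets it would reach the shift table.

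**4. Can the WBC and ANC rows stand in?** Lymphocytes are part of what remains after neutrophils are removed, so lymphocytes ≤ WBC − ANC. With assumed values of WBC 4.0 and ANC 3.5 × 10⁹/L, 4.0 − 3.5 = 0.5 × 10⁹/L, which is the ceiling for lymphocytes and all other non-neutrophil white cells together. The lymphocyte count could lie anywhere from 0 to 0.5, while the ANC stays well above the entry minimum of 1.5 × 10⁹/L (protocol 3.1, criterion 18). The values only illustrate the identity; the documents give no frequency. A shift table also shows grades rather than counts, and the worst WBC and worst ANC may come from different days, so the subtraction cannot be made from the table.

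**5. Is there a baseline floor?** Protocol 3.1 sets minimum haemoglobin, ANC and platelet values but none for lymphocytes. Criterion 21 requires recovery to Grade 1 or better, but only for toxicities of previous therapy. Baseline lymphocyte grade can thus vary, and a baseline-to-worst display would show that.

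**6. Reach.** About 30 patients are expected in each of two arms (protocol 3.3; the synopsis says up to 30): 2 × 30 = 60 at most. Blood-count frequency differs within the protocol. Sections 5.4.3.3, 5.4.3.5 and 10.6 tie the Day 8 and Day 22 draws, or weekly testing, to Phase Ib; footnote 2 of Appendices A and B has no such limit. Weekly counts should not be assumed for all 60.

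**The case against.** The strongest reply is that little is lost. The listings carry grades and do not depend on adverse event reporting. Reported lymphopenia appears by maximum grade in the TEAE tables, with a separate table for Grade 3 or higher. A qualifying event is in the DLT listing. The shift-table list says what it will include without closing itself, and SAP 8.1 allows further exploratory analyses with reasons in the study report.

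Much of this stands, and it rules out several stronger readings that a reader might infer:

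- **That graded lymphopenia will not be shown at all.** Three planned outputs can show it, as set out above.
- **That investigators are told not to report laboratory findings.** The sentence on clinical syndromes is qualified, and its example is the use of a diagnosis in place of a laboratory term. The same section admits abnormal laboratory findings as adverse events.
- **That every Grade 4 lymphopenia is a DLT.** Under protocol 4.5 the toxicity must be at least possibly related to BBI608 or the combination and fall in the first 28 days of combination treatment, and events attributed to TMZ alone are excluded. (For Arm A the section also assesses the run-in and post-operative periods.) A shift table carries no attribution, so it could not identify DLTs.
- **That an added lymphotoxic effect of BBI608 would be missed for want of this row.** The study is not randomised and both arms receive BBI608 with TMZ. The row could not isolate such an effect.

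What the reply does not remove is the missing count. Listings and descriptive statistics do not tabulate patients by grade, and adverse event tables depend on reporting. An open-ended list permits lymphocytes but commits nobody to them.

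**Conclusion.** The point holds as a minor gap in safety reporting. As written, the SAP plans no laboratory-based summary of worst lymphocyte grade, while it does so for the two toxicities named alongside lymphopenia in the protocol.

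It affects no primary estimate, confidence interval, sample size or dose decision. The number of patients whose lymphopenia would go untabulated cannot be estimated, because the documents give no incidence and no rate of adverse event reporting for laboratory findings.

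The conclusion assumes that the shift tables are programmed from the parameters named. If the table shells, which are not in the documents, already include lymphocytes, only the SAP text needs aligning.

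**What to change.** Add lymphocyte count, in the low direction, to the haematology parameters of the SAP 8.2.4.2 shift table from baseline to worst post-baseline CTCAE v4.0 grade. Include unscheduled values, as the section already does for the other parameters, and state that lymphocyte results are graded in the listing.

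Optionally, compare Grade 4 lymphocyte values in the DLT assessment window with the DLT listing and note the recorded attribution of each. This is a data check only and leaves the DLT definition unchanged.

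The cost is one row in an existing table, from data already collected. No visit, sample or protocol procedure changes.

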8.2.4.3. Electrocardiograms

12-lead ECG with categorical results (Normal, Abnormal [Not clinically significant], Abnormal [clinically significant]) will be summarized by treatment and visit. The shift from baseline to worst post baseline will be produced. A patient listing will also be provided.

8.2.4.4. Physical Exam

Physical examination abnormalities will be summarized for each visit by body system and by treatment group. Patients with clinically significant abnormal findings will be flagged in the data listing.

8.2.4.5. ECOG

ECOG will be summarized in a shift table from baseline to worst post baseline for Full analysis set.

8.2.4.6. Vital Signs

Vital sign data will be summarized by treatment and by visit. Change from baseline will be additionally summarized by treatment group and visit.

Summaries of markedly abnormal vital signs parameters, including blood pressure (BP) and pulse, will be presented by treatment group. Values for vital signs for all patients will be presented in a listing, and patients with markedly abnormal values will be flagged.

Markedly abnormal ranges for vital signs parameters are given in the table below.

Vital Sign Parameter	Markedly Abnormal (Low)	Markedly Abnormal (High)
Systolic BP	Absolute value ≤ 90 mmHg, or a decrease from baseline ≥ 20 mmHg	Absolute value ≥ 180 mmHg, or an increase from baseline ≥ 20 mmHg
Diastolic BP	Absolute value ≤ 50 mmHg, or a decrease from baseline ≥ 15 mmHg	Absolute value ≥ 105 mmHg, or an increase from baseline ≥ 15 mmHg

Pulse	Absolute value ≤ 50 bpm, or a decrease from baseline ≥ 15 bpm	Absolute value ≥ 120 bpm, or an increase from baseline ≥ 15 bpm
BMI	Absolute value ≤ 18 kg/m ²	Absolute value ≥ 25 kg/m ²

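### SAP 8.2.4.6 flags BMI without reference to baseline and joins two blood pressure and pulse criteria with 'or', so the 'markedly abnormal' counts are non-specific; report them by criterion and as new since baseline.

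*SAP*

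**What the plan says.** SAP 8.2.4.6 plans that "Summaries of markedly abnormal vital signs parameters, including blood pressure (BP) and pulse, will be presented by treatment group". The table of limits under that sentence has four rows.

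- Systolic pressure: high is "Absolute value ≥ 180 mmHg, or an increase from baseline ≥ 20 mmHg"; low is "Absolute value ≤ 90 mmHg, or a decrease from baseline ≥ 20 mmHg".
- Diastolic pressure: high is "Absolute value ≥ 105 mmHg, or an increase from baseline ≥ 15 mmHg"; low is "Absolute value ≤ 50 mmHg, or a decrease from baseline ≥ 15 mmHg".
- Pulse: high is "Absolute value ≥ 120 bpm, or an increase from baseline ≥ 15 bpm"; low is "Absolute value ≤ 50 bpm, or a decrease from baseline ≥ 15 bpm".
- BMI: high is "Absolute value ≥ 25 kg/m ²"; low is 18 or below. Neither has a change-from-baseline condition.

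Nothing in the section requires a flag to be new since baseline, to be repeated, or to be reported by the criterion that triggered it. The same section also plans by-visit summaries, by-visit change from baseline, and a listing of all values in which patients with markedly abnormal values are flagged. SAP 7.2 takes as baseline the closest value before first dose, no more than 10 days earlier.

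**The concern.** The BMI row can flag something that existed before the first dose. A patient at BMI 27 throughout is marked high although nothing has happened on study. A patient who falls from 32 to 26 is also marked high and never low, although Protocol 1.7 and 4.3 name diarrhea, nausea and anorexia among the common BBI608 events, so weight loss is the direction of interest.

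In the other three rows, a change alone is enough. Systolic pressure moving from 105 to 125 mmHg is labelled markedly abnormal although neither value is near 90 or 180. Each patient is measured repeatedly against a single baseline reading, so ordinary variation accumulates into flags.

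Other SAP safety sections take baseline into account: laboratory grades (8.2.4.2), ECG (8.2.4.3) and ECOG (8.2.4.5) are shown as shifts from baseline to worst value. At stake is whether a reader of the final report can tell a treatment-related change from a pre-existing value or measurement noise. Protocol 11.2 describes a non-randomized study and both arms receive BBI608 with TMZ, so there is no untreated rate for comparison.

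**Working it through.** The documents state no expected flag rate, so there is no planned figure to reproduce. The limits come from SAP 8.2.4.6. All means and SDs below are assumptions, shown as ranges.

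**BMI.** Share flagged high with no change = 1 − Φ((25 − mean)/SD).

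- Mean 24, SD 4: 1 − Φ(0.25) = 40%.
- Mean 24, SD 5: 1 − Φ(0.20) = 42%.
- Mean 28, SD 5: 1 − Φ(−0.60) = 73%.
- Mean 28, SD 4: 1 − Φ(−0.75) = 77%.

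In an arm of 30 this is 0.40 × 30 = 12 to 0.77 × 30 ≈ 23 patients. The fall from 32 to 26 at constant height is (32 − 26)/32 = 19% of weight, and 26 is still above 25.

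**Blood pressure and pulse, one reading.** If each reading has visit-to-visit SD σ, the change from one baseline reading has SD √2·σ, and the chance of meeting the change criterion c in either direction is 2 × (1 − Φ(c/(√2·σ))). At σ = 10/7/8 for systolic/diastolic/pulse:

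- Systolic: 20/14.14 = 1.41, giving 16%.
- Diastolic: 15/9.90 = 1.52, giving 13%.
- Pulse: 15/11.31 = 1.33, giving 18%.

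**Accumulated over visits.** Protocol 5.4.3 schedules vital signs at Cycle 1 Days 5 and 15, Cycle 2 Days 1 and 15, and Day 1 of each later cycle; 5.6 adds End of Study. Five post-dose sets is therefore a reasonable count for about two cycles. A simulation with no drug effect applied the full SAP rule at each visit. It assumed true means (SD) of 128 (15), 78 (9) and 78 (10), independent visit noise, and a systolic-diastolic noise correlation of 0.6.

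| Visit SD (sys/dia/pulse) | High systolic | High diastolic | High pulse | Any blood pressure or pulse flag |
|---|---|---|---|---|
| 6/4.5/5 | 4% | 5% | 6% | 29% |
| 8/5.5/6.5 | 14% | 11% | 17% | 62% |
| 10/7/8 | 24% | 22% | 28% | 85% |
| 12/8/10 | 34% | 30% | 39% | 95% |

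Over 3 to 12 visits the last column runs from 20% to nearly 100%. At five visits the absolute limits alone would flag 6-25%, so the change criterion produces most of the flags.

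**Does the flag still respond?** With a true rise of 10 mmHg in systolic pressure, the share with a rise of 20 mmHg or more goes from 4% to 34% (SD 6), 13% to 47% (SD 8), 24% to 55% (SD 10) and 34% to 61% (SD 12). The signal is diluted but present.

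**The case against.** A reader might infer that most patients will be flagged under no effect and that the table therefore cannot show harm. The documents do not support that.

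- They give no visit-to-visit SD, BMI distribution or expected flag rate. The table sets limits by parameter and direction and specifies no pooled count. One parameter in the high direction gives 4-39%, which is not most patients, and even the pooled blood pressure and pulse figure falls to 29% at low variability.
- The flag rate rises clearly with a true shift, as shown above.
- True outliers are not lost. The 'or' rule flags every value beyond an absolute limit, and the listing prints all values. The patient who goes from BMI 32 to 26 should also appear in the weight change summary, since the protocol counts weight among the vital signs. Adverse events are graded by CTCAE separately.
- A sensitive screen backed by a full listing is a defensible choice in a small early-phase study. SAP 4.1 plans no hypothesis test, the documents attach no dosing or stopping decision to these flags, and the lack of a control affects every safety table here.

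All of this stands, and it limits the point to the usefulness of one descriptive output. It does not answer the BMI row, where a flag present before dosing cannot reflect treatment, or the pooling of two different criteria into one label.

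**Conclusion.** The point holds as one about specificity. The BMI flag ignores baseline and would mark about 40-77% of patients high with no change, if mean BMI is 24-28 with SD 4-5. The blood pressure and pulse flags would reach about 29-95% of patients on at least one parameter, and 4-39% for a high flag on any single parameter, with no drug effect at five visits and the assumed SDs. With no reference rate, such percentages are hard to interpret.

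The reading of the table is certain; the sizes depend on the assumed distributions. The consequence is confined to a descriptive safety table and listing flag. The primary endpoint, the DLT rules and the other safety summaries are unaffected.

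**What to change.** In the SAP 8.2.4.6 table and its accompanying text:

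1. Count a BMI flag only when a post-baseline value moves from within to outside the limit, or replace the row with percent change in weight from baseline, with the cut-off chosen by the sponsor. The first option alone would still not register the fall from 32 to 26; weight change would.
2. For blood pressure and pulse, keep both criteria but tabulate them separately: patients beyond the absolute limit, and patients with the stated change. Count the absolute-limit flag only when the baseline value was not already beyond that limit.

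Do not replace 'or' with 'and'. That would unflag large changes inside the limits (systolic 110 to 175), and also values beyond the SAP's own limits reached by a smaller change (165 to 182, or 108 to 89).

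No new data are needed, because weight is already in the vital-sign sets. The cost is a slightly longer table and minor reprogramming.
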